5. STATISTICAL DESIGN AND CONSIDERATIONS

A. Design

The study will include a control and experimental group. Briefly, the control group consists of healthy, normal-weight individuals and the experimental group consists of obese individuals. After passing an

initial screening, eligible participants will be asked to come in for the first of two visits. During the first visit, informed consent will be reviewed, and the informed consent form will be signed. Subsequently, vital signs, patient history, blood, and other baseline measures will be taken. If the urine pregnancy test and A1C test (< 6.5%) confirm the initial screen results, and if the physical exam and history findings are satisfactory, participants will receive a single dose of Pneumovax 23. The participants will then return for one additional blood draw 4-6 weeks after the first visit. The participants will be physically present for a total of 2 visits and will experience 2 total blood draws. If at any time participants become pregnant, diabetic, or are found to have any conditions listed in the exclusion criteria as revealed by CBC, CMP, or physical exam, then subjects will be indicated as screening failures and will not be included in data analysis due to failure to meet inclusion criteria.

B. Hypotheses

Primary Hypothesis (stated as null): Levels of antibodies to serotypes in Pneumovax 23, in pre- and post- vaccination in healthy BMI individuals and obese individuals are identical.

Secondary Hypothesis (stated as null): Levels of pro- and anti-inflammatory cytokine levels pre- and post- vaccination in healthy weight obese and groups are identical.

Tertiary Hypothesis (stated as null): The perceived level of stress, loneliness and social support will be the same between the healthy weight and obese groups or between groups with different immune responses to the vaccine.

Quaternary Hypothesis (stated as null): Those who carry STING variants and those who are wildtype STING carriers will not have differing immune responses to Pneumovax 23.

C. Statistical Methods

To test the primary hypothesis, we will use the Mayo criteria for positivity of 23 titers, with the primary outcome being the number of positives. We shall employ a two-sided ANCOVA, adjusting for age and gender to compare the obese cases to the non-obese controls. Secondarily, we will compare the 23 individual quantitative titers by similar ANCOVA analyses. Other endpoints will be analyzed in a similar manner as tertiary outcomes.

D. Randomization

No randomization will be done in this study.

E. Sample Size

We expect that 23 evaluable obese participants and 23 evaluable normal weight participants will complete the study. To accommodate for 20% attrition rate we will recruit 28 obese participants and 28 normal participants for a total of 56 eligible subjects. Additionally, to accommodate for individuals unable to participate due to exclusion criteria or individuals eliminated post-enrollment due to screening failure (e.g., CBC/CMP abnormalities), we plan to screen an additional 30 subjects. This accounts for a total of 86 individuals screened. Using information from the 2013-2014 MD-PhD study, we compared those with BMI <25 vs. those with BMI > 25. The distribution of Positive titers amongst the 14 was as follows:

BMI	5	6	7	8	9	10	11	12	Total
<25	1	2	0	2	2	1	4	2	14
>25	0	2	3	0	1	1	0	0	7

This should be viewed as conservative, as we will have greater separation of BMI values than the prior study. The actual gain in power cannot be quantified.

F. Technical Support

Under a CTSI voucher, [name] assisted with the statistics and data analysis. [name] co-authored the statistical section with the students. We will use CTRB facilities for blood draw, temporary tissue storage, and basic lab protocols. The laboratory of [name], MD, will be used to perform experimental procedures including the ELISA assays for IgG quantification.

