Obesity (a body mass index ≥ 30 and waist to hip ratio of at least 0.9 in males and at least 0.85 in females) has been correlated with higher mortality risk and is associated with a proinflammatory state (e.g. elevated levels of TNF-alpha and interleukin-6). Obesity has also been associated with a lower immune response to various types of vaccination (e.g. influenza, hepatitis B, tetanus). As the prevalence of obesity increases, so does the need for a deeper mechanistic understanding of how obesity attenuates vaccination response. It is important to assess the effect of obesity on the immune response to vaccines. The pneumococcal polysaccharide vaccine (Pneumovax 23) is a safe method for stimulating an immune response and its effect on obesity has not been elucidated. As a growing population of obese individuals inevitably age and become susceptible to pneumococcal infections, it is important to consider how obesity may impact the efficacy of Pneumovax 23. We hypothesize that a chronically stressed immune system in obese individuals will be unable to respond as well to vaccination compared to individuals with a BMI between 22 and 25. We will utilize a prospective cohort design. We will also conduct various surveys to examine psychosocial factors that may influence the interaction between obesity and immune response to vaccination. We will also perform genotyping of STING to assess how it may influence the relationship between obesity and immune response to vaccination.

2. HYPOTHESIS AND SPECIFIC AIMS:

The primary objective of this study is to demonstrate the effect of obesity on the immune system's ability to mount a protective immune response against the Pneumococcal Polysaccharide Vaccine (Pneumovax 23).

Primary Hypothesis (stated as null): Levels of antibodies to serotypes in Pneumovax 23 in pre- and post- vaccination in individuals with a BMI between 22 and 25 and obese individuals are identical.

Secondary Hypothesis (stated as null): Levels of pro- and anti-inflammatory cytokine levels pre- and post-vaccination in individuals with a BMI between 22 and 25 and obese individuals are identical.

Tertiary Hypothesis (stated as null): The perceived level of stress, loneliness, social support, and dispositional optimism will be the same between the group of individuals with a BMI between 22 and 25 and the group of obese individuals, or between groups with different immune responses to the vaccine.

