Quaternary Hypothesis (stated as null): Those who carry *STING* variants and those who are wildtype *STING* carriers will not have differing immune responses to Pneumovax 23.

Specific Aim 1: Quantify changes in the adaptive immune response to Pneumovax 23 by measuring specific antibodies to Pneumovax 23 antigens pre- and post-vaccination in the group of individuals with a BMI between 22 and 25 and the group of obese individuals.

Specific Aim 2: Quantify changes in the inflammatory immune response to Pneumovax 23 by measuring C-reactive protein (CRP) and cytokines pre- and post-vaccination in the group of individuals with a BMI between 22 and 25 and the group of obese individuals.

Specific Aim 3: Determine if perceived stress, loneliness, social support, and dispositional optimism are associated with adaptive immune response to Pneumovax 23.

Specific Aim 4: Determine how *STING* genotypes may affect the adaptive immune response to Pneumovax 23.

3. BACKGROUND AND SIGNIFICANCE:

Pneumococcal infections are a leading cause of adult and childhood hospitalization and mortality with an estimated 1.6 million deaths occurring annually.^{1,2} Prophylactic measures against pneumococcal infections exist in the form of a vaccine called Pneumovax 23. While Pneumovax 23 is approved for use in all adults 50 years or older and individuals as young as 2 years who are at increased risk for infection, the vaccine is recommended for all adults 50 years and older or adults age 19 to 64 with conditions or treatments that affect the immune system.³ These recommendations were developed, in part, from a 14-year cohort study comparing the proportion of pneumococcal infections caused by varying pneumococcal serotypes included in vaccinated and unvaccinated individuals.⁴ Pneumovax 23 had an overall efficacy rate of 57% in preventing pneumococcal infection. In addition to recommending the vaccine to the elderly, the vaccine is also recommended for individuals who have been identified as being at higher risk for contracting pneumococcal pneumonia, such as those infected by human immunodeficiency virus.⁵ Increased weight gain and a high body mass index have been associated with an increased risk for contracting pneumococcal pneumonia, suggesting it is desirable to provide effective vaccination of this susceptible population.⁶

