2. Study Design: Participants will be asked to fast after midnight prior to the first blood draw. A baseline blood draw (39 mL) will be performed for each participant. Pneumovax 23 will then be administered into the deltoid muscle by the CRC nurses; needle length will be adjusted according to distance from skin surface to muscle bundle. The Pneumovax 23 vaccine will be provided by the University of Florida Investigational Drug Services. They receive their commercial products from McKesson Pharmaceuticals. Effort will be taken to ensure that all participants receive the same lot number of Pneumovax 23.

Blood will be drawn 4-6 weeks following vaccination, as primary antibody production peaks during this time frame.⁴⁰ At that time, a total of 33 mL of blood will be drawn for analyses of antibody and cytokine levels. Table I illustrates what assays will be performed on the blood drawn at each time point and Table II illustrates the schedule of each blood draw. Figure 2 outlines a progression of events that will occur during both the screening and the first visit.

[figure not shown]

Figure 2. Progression of events during Visit 1:
Consenting, screening confirmation, blood draw,
vaccination, survey administration, and payment distribution

B. Measurements to be Collected

1. Basic Demographics (e.g. gender, age, race, ethnicity, education, etc.) will be collected.
2. Height, weight and hip-waist circumference will be collected.
3. Baseline Characteristic Assessments: Pregnancy will be evaluated by urine test, and hemoglobin A1C level will be determined with a portable finger-prick monitor.
4. Whole Blood Lab Assays: The following whole blood lab assays will be sent to and performed by Shands Laboratory: total IgG titers, complete metabolic panel, erythrocyte sedimentation rate, and complete blood count (CBC).
5. Anti-pneumococcal Antibodies: IgG antibody titers specific for each serotype in Pneumovax 23 (i.e. 1, 2, 3, 4, 5, 6B, 7F, 8, 9N, 9V, 10A, 11A, 12F, 14, 15B, 17F, 18C, 19F, 19A, 20, 22F, 23F, and 33F) will be analyzed using a panel ordered through the Mayo Clinic.
6. Serum Analyte Measurements: ELISA will be used to measure various acute phase reactants (e.g. TNF, C reactive protein, interferons, interleukins, etc.) and Ig subclasses. If significant

differences are not observed between arms then a cytometric bead assay may be employed. ELISAs will be performed in [name] lab.

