7. TIME AND EVENTS

Potential participants will be screened via phone or REDCap surveys. If a potential participant qualifies after the screening survey, a visit to the UF campus CRC building will be scheduled.

Upon arrival at the CRC, informed consent will be reviewed, and the informed consent document will be signed. Following this enrollment, the participant will have vitals checked and will undergo an HbA1C fingerprick test, a urine pregnancy test, a physical exam, and a comprehensive medical history. If the participant still meets inclusion criteria, then screening accuracy is confirmed. Participants who are found to be screening failures will be told they are no longer eligible for the second part of the study and be given a gift card. For those that continue, blood will be drawn and sent to respective locations outlined in Table 1. Subsequently, the Pneumovax 23 vaccine will be administered. Following administration of the vaccine, four questionnaires will be administered; simultaneously while completing the forms, the

participant will be monitored for adverse side effects to the vaccine. Payment will be administered after the surveys, and the subsequent visit will be scheduled.

At the second visit 4-6 weeks following the first, blood will be drawn once more and distributed to the locations outlined in Table 1. After the blood draw, the participant will be compensated and thanked profusely for participating in the study. Completion of visit two marks the culmination of the study for that particular participant. Data analysis will ensue once 56 participants have progressed through the study. The events occurring in the study are outlined in Table 3.

Table 3. Proposed Schedule

	Events	Prior to Visit 1	Estimated Time (min)	Visit 1: Day 0	Visit 2: Wk 4-6
Screening	Contact with participants by phone or email	X	10		
	Set up REDCAP and chart for each participant	X	20		
	Screening via phone or REDCAP survey	X	10		
	Instructions email or phone call	X	10		
Visit 1	Informed Consent		20	X	
	Urine Pregnancy Test		10	X	
	A1C		5	X	
	Medical History		10	X	
	Physical Exam,		10	X	
	Waist/Hip Ratio		2	X	X
	Vitals		2	X	X
	Blood draw for CMP, CBC, and ESR		6	X	
	Pneumvax23 Vaccination		5	X	
	Blood draw for total IgG, serotypes, and cytokine assays		6	X	X
	Questionnaire Completion (4 surveys)		30	X	
	Instructions for next visit		5	X	
	Payment		5	X	X
	Total Time Per Visit (min)			114	20-30

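### The protocol's primary count of positive titres has no visit and no baseline adjustment, and its primary null also covers pre-vaccination levels

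*Protocol*

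**What the plan says.** **Outcome and model.** Protocol 5.C judges the 23 titres by the Mayo positivity criteria, "with the primary outcome being the number of positives". The model follows: "We shall employ a two-sided ANCOVA, adjusting for age and gender to compare the obese cases to the non-obese controls". Neither sentence gives a visit, a change score or a baseline covariate.

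**Two counts per participant.** Table 3 in section 7 marks "Blood draw for total IgG, serotypes, and cytokine assays" for both visits, and Table 1 in section 4.B agrees.

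**The null.** Section 5.B puts it as "Levels of antibodies to serotypes in Pneumovax 23, in pre- and post- vaccination in healthy BMI individuals and obese individuals are identical". Section 2 words it almost identically: "Levels of antibodies to serotypes in Pneumovax 23 in pre- and post- vaccination in individuals with a BMI between 22 and 25 and obese individuals", again stated to be the same in both groups.

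**Hints about timing.** Specific Aim 1 points to change: "Quantify changes in the adaptive immune response to Pneumovax 23 by measuring specific antibodies to Pneumovax 23 antigens pre- and post-vaccination". Section 4.A.2 points to the second visit: "Blood will be drawn 4-6 weeks following vaccination, as primary antibody production peaks during this time frame". Section 4.F describes the primary outcome as relative group differences in immune markers, with no visit.

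**The SAP.** Its primary outcome is the serotype-specific IgG response, and its primary analysis is an ANCOVA of fold change in titres, controlling for sex and age. It still bases power on the number of positive titres, and neither that count nor the prior-study table carries a visit.

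**The concern.** The stated objective is whether obesity affects the ability to mount a response to the vaccine. A difference present before vaccination does not bear on that, yet it makes the null as worded false.

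The two reasonable readings of the count are positives at Visit 2 and the change from Visit 1. Neither handles baseline well as written. A Visit 2 count includes serotypes that were already positive. A change in count is capped by them, because a serotype already positive cannot convert. With no randomisation and no baseline covariate, unequal starting positivity enters both readings, with opposite sign. Excluding prior pneumococcal vaccination and prior pneumonia should lower pre-existing positivity, but nothing in the documents shows that it removes it.

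**Working it through.** **1. The plan's own figure.** From the prior-study table:

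- BMI <25: mean 129/14 = 9.21, SD 2.33
- BMI >25: mean 52/7 = 7.43, SD 1.51
- Difference: 1.79
- Pooled SD: √[(13 × 2.33² + 6 × 1.51²)/19] = 2.10
- Standardised difference: 0.849

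A two-sided t test at 0.05 with 23 per group then has power 0.804. The stated 23 per group is reproduced, and the sample size is not in question here.

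**2. Direction of the bias.** Let a proportion p of the 23 serotypes be positive at Visit 1, and let a proportion c of the negatives convert, with the same c in both groups (equal response). If the groups differ at baseline by Δp, the expected group differences are:

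- Visit 1 count: 23 × Δp
- Visit 2 count: 23 × (1 − c) × Δp
- Change in count: −23 × c × Δp
- Visit 2 given Visit 1: zero, because the expected Visit 2 count is 23c + (1 − c) × (Visit 1 count) in both groups

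For any c between 0 and 1, Visit 2 and change have opposite signs. With c = 0.5 and Δp = 0.10, Visit 2 gives 23 × 0.5 × 0.10 = +1.15 positives for the group that started higher, and change gives −1.15.

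**3. Size.** Assumptions, none of them from the documents: 50% conversion in both groups, conversion varying between people with the same intra-person correlation as baseline positivity, positivity measured without error, and no age or sex effects. There are 23 per group and tests are two-sided at 0.05. Unadjusted counts are compared by t test. The adjusted analysis is ANCOVA of the Visit 2 count on group and Visit 1 count.

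| Assumed baseline positivity | Intra-person correlation | Expected difference: Visit 2 / change | Visit 2 rejects | Change rejects | Adjusted rejects |
|---|---|---|---|---|---|
| 25% vs 35% | 0.1 | +1.15 / −1.15 | 17% | 17% | 4% |
| 20% vs 35% | 0.05 | +1.73 / −1.73 | 44% | 44% | 5% |
| 25% vs 28% | 0.1 | +0.35 / −0.35 | about 6% | about 6% | about 5% |

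The second row has both a wider gap and a lower correlation, so not all of the rise from 17% to 44% is due to the gap. The third row shows that the problem nearly disappears when the groups start close together.

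**The case against.** **The intended reading is clear enough.** The objective, Aim 1 and the timing of the second draw all point to response, so nobody would analyse Visit 1 alone as primary. That is fair, and the live ambiguity is Visit 2 versus change. But these hints point to different contrasts, and the null still names pre-vaccination levels.

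**The SAP settles it.** Fold change uses both visits and rules out a Visit 1-only test. If the SAP governs, the practical effect is limited. It gets there by replacing the variable, so the protocol's count and null stay as they are.

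**The Mayo criteria may fix the time point.** If positivity means a rise or a post-vaccination threshold, the visit is implicit. The criteria are not reproduced, so this cannot be ruled out.

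**Baseline adjustment is debatable in non-randomised groups.** This stands in part. The 4-5% follows from defining equal response as equal conversion of negatives. If equal response meant an equal rise in count, the change score would be the unbiased one. In a normal model with the prior study's difference (1.79) and SD (2.10) placed at baseline and carried forward, change rejects about 5% and the unadjusted Visit 2 count about 80%. The unadjusted Visit 2 count fails under either definition. Because a positive serotype cannot convert, conditioning on Visit 1 suits a capped count better. Misclassification leaves some bias: with an assumed 10-15% at each visit and 20% vs 35% baseline, the adjusted analysis shows a spurious 0.36 to 0.45 positives and rejects 6.7-7.7%.

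**Two stronger readings do not hold.** A reader might infer that the visit chosen reverses the trial's conclusion. In this model Visit 1 and Visit 2 favour the same group; the opposite sign is between Visit 2 and change. Both are significant in opposite directions in only 0.6% of runs at 25% vs 35%, and 12% at 20% vs 35%. A reader might also infer an inflated family-wise error. Protocol 5.C plans one outcome and one two-sided ANCOVA, and no document proposes testing each visit and claiming success on either.

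**Conclusion.** The point holds as a defect in how the protocol defines its primary outcome and null. On the text alone, the count has no visit, the model has no baseline term, and a baseline difference falsifies a null meant to test vaccine response.

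The numerical effect is conditional. With equal response, false rejection by either unadjusted reading runs from about 6% to 44% over the baseline gaps examined, with biases in opposite directions, against 4-5% with adjustment. These figures rest on assumed baseline rates, conversion and correlation. The practical weight falls if the SAP's fold change is the governing primary analysis, or if the Mayo criteria already fix a time point.

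**What to change.** - In protocol sections 2 and 5.B, restrict the primary null to vaccine response and remove the pre-vaccination comparison from it.
- Wherever the count is kept as an outcome, in 5.C or the SAP, define it as the number of Mayo-positive titres at Visit 2, with the Visit 1 count added to age and sex as a covariate. State the positivity rule.
- Report the Visit 1 comparison descriptively with the baseline characteristics.
- Align the protocol and SAP on which variable is primary.

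Both panels are already collected, so the change is one of wording. It costs one degree of freedom and gives up a pre-vaccination difference as a primary finding. Some residual confounding remains if positivity is misclassified at baseline. If the prior study's difference and SD are taken to apply to the Visit 2 count, 23 per group still gives power of about 0.80 before any covariate adjustment.

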1. Study Participants: For this study, we will recruit 86 participants. However, not all of those participants will qualify for the study and we estimate that, of the 86, a total of 56 people will qualify for the study. This accounts for a 20% attrition rate, reaching a desired 46 participants based on our power analysis. The 56 participants will be separated into two groups, each consisting of 28 participants. Group 1 will contain individuals with a BMI between 22 and 25. Group 2 will contain obese individuals, defined as a $\text{BMI} \geq 30$ and waist to hip ratio of at least 0.9 in males and at least 0.85 in females. Study participants will be between the ages of 18-35 and in good health.

Recruitment Process: Participants will be recruited in the study under the title, “Pneumonia Vaccine Study.”

Flier - Fliers will be posted on boards and walls at the University of Florida Health Science campus and all affiliated or satellite sites as well as in busy areas with lots of foot traffic within the community (Butler Plaza, Publix, Oaks Mall, etc.).

IDR - If we require more numbers, the IDR will be utilized to contact individuals who fit the criteria for our study. Our co-investigators will be calling each eligible person.

Inclusion Parameters: Alachua county resident

Said yes to recontact for research studies

Obesity diagnosis

Exclusion Parameters: Diabetes, complicated

Drug Abuse

Weight Loss

AIDS

Alcohol abuse

Renal failure

Solid tumor without metastasis

Metastatic cancer

Liver disease

Lymphoma

Leaves 150 possibly eligible participants to contact

ResearchMatch – ResearchMatch allows researchers to search for volunteers who have identified themselves as being interested in participating in research. Interested participants create a “profile”

with basic health information that allows researchers to search for potential participants that meet certain criteria. If a match is identified, the potential participant can be sent details about the study opportunity and can then choose whether to provide their contact information to the researcher. There is an estimated 30 potential participants to contact who are located within 25 miles of UF, between 18 and 35 years of age, have a BMI of 30+, do not smoke, and report no medical conditions.

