The primary outcome measure for the power calculation was the number of positive pneumococcal titers using data from Wildes et al. (2019). This study included a range of BMIs under 30. By comparing the number of positive titers between those with a BMI < 25 and > 25, we expect that 23 evaluable obese participants and 23 evaluable normal weight participants will provide enough power for the study (see the distribution of positive titers below in Table 1) at a significance level of $\alpha = 0.05$ for a 2-sided t test at 80% power. We consider this estimation to be conservative, as we expect that having a greater separation of BMI values than Wildes et al. will provide greater power. The actual gain in power cannot be quantified.

Table 1. The distribution of positive titers amongst the 14 in Wildes et al. study was as follows:

BMI	5	6	7	8	9	10	11	12	Total
<25	1	2	0	2	2	1	4	2	14

>25	0	2	3	0	1	1	0	0	7
-----	---	---	---	---	---	---	---	---	---

Aims and objectives

The aim of this project is to investigate the effect of obesity on the immune system's ability to mount a protective immune response against the pneumococcal polysaccharide vaccine (Pneumovax 23).

Outcomes

Primary outcome: Vaccine response as measured by serotype-specific IgG antibody responses against the 23 pneumococcal serotypes (i.e., 1, 2, 3, 4, 5, 6B, 7F, 8, 9N, 9V, 10A, 11A, 12F, 14, 15B, 17F, 18C, 19A, 19F, 20, 22F, 23F, 33F)

Statistics:

When comparing between populations (ie. baseline characteristics table), normality was first assessed by the Shapiro-Wilk test, then followed by either an unpaired 2-sided t test or a Wilcoxon's signed-rank test for parametric data or nonparametric data, respectively. Chi-square tests determined differences in categorical data (i.e. sex, ethnicity). For our primary analysis, we will use an ANCOVA to test for differences in fold change titer levels across groups (nonobese and obese), controlling for sex and age. All hypothesis tests were 2-sided where a P value < 0.05 was considered significant.

To assess the role of the STING genotype, a secondary analysis will be done using 2-way ANOVA of the fold change in titer levels between the wildtype, R232/R232, and HAQ carrier genotypes. Likewise, to assess the role of psychosocial variables, we will also be using an ANOVA or regression, as appropriate. For secondary analyses, we will not perform any multiple testing corrections for P values.

References

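### 28 recruited per group does not leave 23 evaluable after 20% attrition; it tolerates about 18% (a minor arithmetic inconsistency with a marginal effect on power)

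*Protocol*

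**What the plan says.** Protocol section 5.E sets the evaluable target: "We expect that 23 evaluable obese participants and 23 evaluable normal weight participants will complete the study". It then gives the allowance for losses: "To accommodate for 20% attrition rate we will recruit 28 obese participants and 28 normal participants", for 56 eligible participants in total. Ineligibility and screening failure are handled separately in the same section: "we plan to screen an additional 30 subjects", which brings the number screened to 86.

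Protocol section 4.A.1 (Study Participants) makes the same claim for the totals. Of 86 people, 56 are expected to qualify, and: "This accounts for a 20% attrition rate, reaching a desired 46 participants based on our power analysis".

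The error rate and power target are stated only in the SAP, under Sample size calculation. It gives a significance level of 0.05 "for a 2-sided t test at 80% power", with 23 evaluable per group. It states no attrition rate, enrolment number, effect size or SD. Both documents tabulate the same pilot counts of positive titers.

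Protocol section 7 (Time and Events) adds: "Data analysis will ensue once 56 participants have progressed through the study".

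**The concern.** Three figures are tied together in two places: 56 recruited, 20% attrition and 46 evaluable. Any two of them fix the third, and the stated three do not agree. The separate allowance of 30 for screening failure does not absorb the difference, because it covers the step from 86 to 56, before attrition is applied.

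At stake is whether the sample-size statement is correct as written. Because 23 per group is only just enough for 80% power under the most direct reading of the SAP's calculation, it is also worth checking how far power falls if attrition really is 20%.

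**Working it through.** **Inputs**
- Evaluable target: 23 per group, 46 in total (Protocol 5.E and 4.A.1).
- Attrition: 20% (same sections).
- Recruited: 28 per group, 56 in total (same sections).
- Test: two-sided t test, alpha 0.05, 80% power (SAP, Sample size calculation).
- Effect size and SD: not stated; derived below from the pilot table.

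**Step 1: reproduce the evaluable target of 23.** From the pilot table:
- BMI <25: n = 14, sum 129, mean 9.214, SD 2.326.
- BMI >25: n = 7, sum 52, mean 7.429, SD 1.512.
- Difference = 1.786.
- Pooled SD = √[(13 × 2.326² + 6 × 1.512²)/19] = 2.104.
- Standardised difference d = 1.786/2.104 = 0.849.

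A two-sample t test at two-sided 0.05 and 80% power needs 22.78 per group, so 23. The plan's figure is reproduced. (The normal approximation gives 22.)

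**Step 2: apply the stated attrition to the stated recruitment.**
- Per group: 28 × (1 − 0.20) = 22.4, which is 0.6 below 23.
- Total: 56 × (1 − 0.20) = 44.8, which is 1.2 below 46.

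**Step 3: find the attrition that the stated numbers allow.**
- 1 − 23/28 = 1 − 46/56 = 17.9%.
- In whole people, losing 5 of 28 (17.9%) leaves 23; losing 6 of 28 (21.4%) leaves 22.

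**Step 4: find the recruitment that 20% would require.**
- 23/(1 − 0.20) = 28.75, so 29 per group and 58 in total.
- Check: 29 × 0.8 = 23.2.
- For comparison, 23 × 1.2 = 27.6, which rounds up to the protocol's 28. Truncating 28.75 would also give 28.

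**Step 5: effect on power** (two-sided alpha 0.05, difference 1.786):

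| Method | 22 per group | 22.4 per group | 23 per group |
|---|---|---|---|
| t test, pooled SD 2.104 | 78.5% | 79.3% | 80.4% |
| Normal approximation, pooled SD 2.104 | 80.4% | 81.1% | 82.1% |
| t test, average-variance SD 1.962 | 83.9% | 84.6% | 85.5% |
| t test, BMI <25 SD 2.326 | 70.1% | 70.9% | 72.1% |

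The average-variance SD is √[(2.326² + 1.512²)/2] = 1.962. Within any row, going from 23 to 22.4 costs about 1 percentage point and going to 22 costs about 2. Between the t-test rows at 23 per group, power runs from 72.1% to 85.5%, a spread of about 13 points that comes from the SD alone.

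**The case against.** The strongest case on the other side has five parts.

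- **The gap is a fraction of a person.** No whole-number loss from 28 is exactly 20%, so 20% could be a rounded 17.9%. If each participant independently had a 20% chance of dropping out, 28 recruits would still leave at least 23 with probability of about 50%. This bears on importance. It does not make the sentence correct, since the protocol gives 20% as the planning rate and 46 as the result.
- **The formula is not shown.** A reader might infer that the protocol multiplied by 1.2. The documents do not support stating that as fact, because truncating 28.75 also gives 28. The inconsistency is the same whichever route was taken.
- **Power.** A reader might go further and infer that the trial misses its 80% power. The documents do not support that either. They give no effect size or SD, so every power figure here depends on a choice made from the pilot table. Under the normal approximation or the average-variance SD, power at 22 per group stays above 80%; with the BMI <25 SD it is below 80% even at 23. The pilot is 14 against 7 people, and an approximate 95% interval for d runs from roughly −0.1 to 1.8. A difference between 80.4% and 79.3% has no decision value against that. This objection stands.
- **The estimate is called conservative.** Both documents say so, on the ground that BMI separation will be wider than in the pilot, though they add that the gain cannot be quantified. It is a reason not to press the power point, but it has no bearing on the attrition arithmetic.
- **56 may mean completers.** The sentence in section 7 follows the description of visit two and can be read that way, in which case there would be no shortfall. But sections 4.A.1 and 5.E both make 56 the number before attrition. The completer reading would therefore contradict them rather than resolve the point.

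**Conclusion.** The attrition statement is wrong as written in Protocol sections 4.A.1 and 5.E. That conclusion needs only the protocol's own numbers and the usual meaning of attrition as a proportion of those recruited. The shortfall is 0.6 per group (1.2 in total) in expectation, equivalent to one more recruit per group (29 instead of 28).

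The effect on power is marginal: about 1 to 2 percentage points under a pooled-SD t test on the pilot counts, and smaller than the effect of choosing a different SD. No endpoint or analysis method is affected. This is a minor consistency correction and is not evidence of a materially underpowered trial.

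**What to change.** Restate the figure in Protocol sections 4.A.1 and 5.E in one of two ways:

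1. Keep 28 per group and 23 evaluable, and say that this tolerates about 18% attrition (5 of 28 per group).
2. Keep 28 per group and 20%, and state about 22 evaluable per group (about 45 in total), with roughly 78% to 79% power under a pooled-SD t test on the pilot counts. The 23 per group in the SAP's sample-size section would then need to be aligned.

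Either costs a sentence in each section and no extra participants. The first is simpler because it leaves the SAP untouched. If the sponsor prefers to keep both 20% and 23, the numbers become 29 per group and 58 in total, with 88 screened if the separate allowance of 30 is unchanged (58 + 30). That costs two more participants.

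In either case, reword the sentence in Protocol section 7 so that it is clear whether analysis starts when 56 have been recruited and followed as far as they will go, or when 56 have completed visit two.
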